### Biomarker Studies

 Urine specimens for biomarker studies will be collected before the first treatment, before and after the  $4^{th}$  treatment, and at the 34 week time point. Markers to be evaluated are outlined in Section 7. The primary goal of these studies is to evaluate changes in marker levels over time and evaluate the associations between these changes and both treatment and overall patient responses. Due to the large number of markers being evaluated, in order to protect against an inflation in Type I error rates due to multiple comparisons, the sample size and power calculations below utilize an overall Type I error of  $\alpha$ =0.01. It is recognized that these evaluations are primarily exploratory, and that measures that demonstrate promise as laboratory markers may require further evaluation in another clinical trial setting.

Analyses on which sample size estimates are based will consist of two primary types. The first type will involve paired comparisons of changes from baseline to 34 weeks, within subgroups defined by treatment arm and/or response to therapy (as defined by the primary endpoint). These analyses will utilize a paired t-test. The required sample sizes to detect changes of a given magnitude, in units of standard deviations of the change (s.d.), are given in the table below. The second set of analyses will compare these changes between subgroups defined by treatment arm and/or response to therapy using a two-sample t-test. The required sample sizes to detect differences in the changes, also in units of s.d., are also in the table. These calculations assume 80% power with a two-sided  $\alpha$ =0.01

, 5												
Cina of	Required Sample Sizes											
Size of	Paired t-test to	Two-Sample t-test to Compare Two Groups										
Difference	Compare Changes	1:1 Ratio	o of Group	1:2 Ratio	of Group							
(in units of s.d.)	Within a Group	S	izes	Sizes								
1.0	15	50	(25 + 25)	57	19 + 38							
0.9	18	60	(30 + 30)	69	23 + 46							
0.8	21	76	(38 + 38)	84	28 + 56							
0.7	27	98	(49 + 49)	111	37 + 74							
0.6	36	130	(65 + 65)	147	49 + 98							
0.5	50	186	(93 + 93)	210	70 + 140							
0.4	76	> 260		> 260								
0.3	130	> 260		> 260								
0.2	> 260	> 260		> 260								
0.1	> 260	> 260		> 260								

 In addition to the two-sample tests above, changes in marker values over time will be compared with changes in symptom scores including the global assessment of response, pain/urgency scales, and scores on the symptom indices. Depending on the nature of the symptom outcome, various regression models including linear regression, logistic regression, and regression models for ordinal outcomes will be used to evaluate the associations between marker changes and symptom changes controlling for treatment and other relevant baseline measures. The statistical methods for these analyses are described in the previous section.

## 13.5.1 Data Safety and Monitoring and Interim Analyses

In addition to the final data analysis and standard monitoring for adverse events and data quality, one interim analysis will be conducted for the primary safety and efficacy data after approximately one half (n = 130) of the participants have been accrued and followed for 34 weeks. Given the projected accrual rates, it is expected that this will occur approximately fifteen months into the conduct of this study. The results of these analyses will be presented to the External Advisory Committee. The goal of this analysis is to identify major differences among treatment arms that might lead to early study closure for ethical reasons. The endpoints to be considered at the interim time point include the primary response endpoint, toxicity and adverse events, and withdrawal rates. For the primary endpoint, the Lan and DeMets (52) analog to an O'Brien-Fleming boundary (53) will be used to calculate the nominal significance level to which interim p-values are compared. Only an "upper" boundary, which allows for closure in the case of evidence of a treatment difference, will be used at this interim analysis. Assuming this analysis is conducted using 34-week data on 130 participants, corresponding to an information time of 50%, the boundary significance level to which the observed p-value will be compared is 0.0031. As described above, sample sizes have been adjusted to account for this interim monitoring.

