## 4.3 Treatment and Follow-up

In the first phase, patients will be randomized in equal proportions to receive six (6) instillations of either BCG or saline within a 10 week period of time. All patients will be followed for 34 weeks from randomization.

209210

211

212

- A variety of pharmacotherapeutic agents are utilized in the treatment of IC. This study will define as "IC Treatment Medications" those agents medically prescribed for treatment of IC symptoms in patients with an established diagnosis of interstitial cystitis.
- 213 These medications are identified in the following therapeutic categories:
- Tricyclic Antidepressants
- Sedating Antihistamines (H1 Blocker)
- Anticonvulsants
  - Alpha2-Adrenergic Agonist Agents
  - Intravesical therapies (e.g. DMSO, Clorpactin, Heparin)

218219

217

- 220 Prior to randomization, all patients will be stabilized on current medications.
- 221 Medications prescribed for treatment of IC from these therapeutic categories will be
- specifically identified in the patients pre-study diary record and monitored in the patients
- 223 concomitant medication record throughout the study. Additionally, if the patient is taking
- prescribed medications for treatment of IC that are not included in the above categories,
- these medications will also be identified and monitored as IC medications.
- 226
- Patients randomized into the study will be requested to have no change in their pre-study medication regimen for IC throughout the treatment and follow-up period. It is strongly recommended that categories of medications (as listed above), prescribed for the
- treatment of IC, be *avoided* in managing the patients IC symptoms throughout the trial.
- 231 Instead, *breakthrough* medications (as listed in 4.3.1) will be used to manage the patient's
- 232 IC symptoms throughout the trial. Other than the specified intravesical treatment
- administered in this study, the administration of any other intravesical treatment is
- prohibited during the course of this study.

235236

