## **6.2 Study Population and Number of Participants**

The study population for this RCT #2 protocol will be drawn from participants with a diagnosis of IC, confirmed sometime in the past with the results from a cystoscopy/hydrodistention. It is expected that 260 participants will be accrued within a 14 month time period from the start of the study. (See Section 13.2).

Any IC participant presenting with symptoms of urinary frequency in conjunction with urinary pain/discomfort persisting for at least 24 weeks will be considered a candidate for enrollment into the study. Participants must satisfy the following eligibility criteria in order to be entered into this study.

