## 10.3 Treatment Phase One (Visits 1 – 6)

731 732

733 Treatment Visit I should begin within two weeks of Baseline 2 visit with randomization. 734 All attempts should be made to ensure compliance with the visit schedule for treatment. 735 During the treatment phase of the study, BCG or placebo solution will be instilled into 736 the bladder (Appendix C Protocol for Administration of Study Agent). This procedure 737 will be repeated once each treatment for a total of six treatments within a 10 week period 738 of time from the date of randomization. The interval between treatments will be a 739 minimum of 6 days and a maximum of three weeks. No more than 3 weeks may lapse between treatments. Therefore, treatment schedules must take into consideration the

740

741 following:

742 743

744

745

746

- 1. Treatment visits will be scheduled according to patient's tolerability.
- 2. Some patients may not receive all six study treatments.
- 3. All intravesical treatments must be administered within a 10 week visit schedule.
- 4. Treatment regimen will require the interval between treatments to be a minimum of 6 days and a maximum of 3 weeks.

747 748 749

750

751

752

Information obtained during the instillations, as well as a record of treatment follow-up phone call, will be recorded. Patients will be instructed to report any adverse reactions without delay. Intercourse should be avoided during the period of 48 hours following each treatment instillation. Although sexual transmission of BCG has not been reported, it is required that a condom be used in the event of intercourse during this period.

753 754 755

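### On the protocol's own accrual figures, the only scheduled between-arm interim review comes after the last planned randomization, so its stated ethical purpose is largely, though not wholly, defeated

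*Protocol*

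**What the plan says.** Protocol Section 6.2 gives the accrual plan: "It is expected that 260 participants will be accrued within a 14 month time period from the start of the study". Section 13.5.1 schedules a single interim analysis "after approximately one half (n = 130) of the participants have been accrued and followed for 34 weeks", and adds that, given projected accrual, "it is expected that this will occur approximately fifteen months into the conduct of this study". Its goal is to "identify major differences among treatment arms that might lead to early study closure for ethical reasons". The endpoints reviewed are the primary response, toxicity and adverse events, and withdrawal rates. The results go to the External Advisory Committee.

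For the primary endpoint, "the boundary significance level to which the observed p-value will be compared is 0.0031". Stopping is foreseen only for evidence of a treatment difference; there is no futility boundary. Section 13.2 adds 5% to the sample size for this monitoring.

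Section 4.3 sets the follow-up: "All patients will be followed for 34 weeks from randomization". Section 10.3 limits randomized treatment to "six treatments within a 10 week period", counted from randomization. Sections 4.2 and 10.5 then offer week-34 non-responders an open-label BCG course, with follow-up to week 68.

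**The concern.** An interim look meant to allow early closure on ethical grounds protects participants mainly in two ways: it stops further randomization, and it stops randomized treatment in those still receiving it. Both depend on the look coming while people are still being enrolled or treated. Here the stated accrual period is 14 months and the stated look is at about fifteen.

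Efficacy data at week 34 cannot be had earlier, but toxicity and withdrawal during the instillations can. Section 13.5.1 nevertheless ties the only scheduled between-arm comparison of these to the same late date. If BCG, a live organism, caused an excess of toxicity or withdrawal over saline, the first scheduled comparison by arm would come when everyone had been randomized and nearly everyone had finished the course.

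**Working it through.** **Inputs.** 260 participants in 14 months (Section 6.2); trigger of 130 participants with 34 weeks of follow-up, stated at about 15 months (13.5.1); treatment window of 10 weeks from randomization (10.3); planning response rates of 30% and 50% (13.1 and 13.2). Accrual is assumed uniform, with 365.25/12/7 = 4.348 weeks per month.

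**1. The plan's own date.**
- Rate: 260/14 = 18.57 per month.
- 130th participant: 130/18.57 = month 7.0.
- Follow-up: 34/4.348 = 7.82 months.
- Look: 7.0 + 7.82 = month 14.8, which agrees with the stated fifteen.
- Gap after the end of accrual: 14.8 − 14 = 0.8 month, or 1.0 month on the stated date.

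**2. Who can still be protected from randomized treatment.**
- Enrolled at the look: 260 of 260.
- Window: 10/4.348 = 2.30 months, so those still inside it entered after month 14.82 − 2.30 = 12.52.
- Number: (14 − 12.52) × 18.57 = about 27 (11%). At month 15.0 it is about 24.
- If instillations run weekly, so that treatment ends 5 to 7 weeks after randomization, about 3 to 15 remain.
- With one further month for cleaning and review (an assumption; month 16), 0 to 6 remain.

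**3. What the look can still affect.**
- Blinded follow-up: participants not yet at week 34 number 260 − 130 = about 130.
- Open-label Phase 2: expected non-responders are 130 × 0.70 + 130 × 0.50 = 156. About half (78) belong to participants who have not reached the week-34 offer.
- Week 68 is 68/4.348 = 15.6 months after randomization, so no participant has completed Phase 2 or 2R by month 14.8.

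**4. Sensitivity to the accrual pattern.**
- For the look to precede month 14, the 130th participant must enter by 14 − 7.82 = month 6.18, that is, half the sample in the first 44% of the period.
- With N(t) = 260 (t/14)^k, a slower start moves the look to month 15.9 (k = 1.25), 16.6 (k = 1.5) or 17.7 (k = 2). Only front-loaded accrual (k below about 0.85) brings it before month 14.
- If uniform accrual takes A months, the look is at A/2 + 7.82, which precedes A only when A exceeds 15.6. The fraction enrolled at the look is (A/2 + 7.82)/A: 93% at 18 months, 89% at 20 and 83% at 24. That leaves about 17, 28 and 45 participants unrandomized.

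**5. When treatment-phase data become available.**
- First 65 at week 10: 65/18.57 + 2.30 = month 5.8, with 5.80 × 18.57 = 108 enrolled (about 42%).
- First 130 at week 10: 7.0 + 2.30 = month 9.3, with 173 enrolled (66%).
- Allowing the same assumed month for review, 6.80 × 18.57 = 126 (49%) and 10.30 × 18.57 = 191 (74%) would be enrolled when a decision could be made.

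**6. Boundary and sample size.** The Lan-DeMets O'Brien-Fleming-type boundary at 50% information is 0.00305, matching 0.0031. The sample size also reproduces: 103 × 1.20 × 1.05 = 129.8, or 130 per arm.

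**The case against.** A reader might infer that the look cannot serve its purpose at all. The documents do not support that. Section 13.5.1 speaks of closing the study, not only of stopping enrolment, and the study continues to week 68. Closure at month 15 could stop the last instillations, end blinded follow-up for about 130 participants and affect open-label courses not yet begun. An efficacy finding would also bear on the Section 10.5 rule that keeps responders off open-label BCG. This part of the objection stands.

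Nor is safety unmonitored until month 15. Section 13.5.1 places the interim on top of standard adverse-event monitoring. Section 11.1 has adverse-event forms summarized quarterly or as needed, and Section 11.2 sends serious adverse events to the External Advisory Committee. None of these is described as a comparison between arms. Section 13.5.2 refers to a separate Data Analysis and Monitoring Plan, not at hand, which may add reporting detail; that absence is not criticized here. The point rests only on the schedule that 13.5.1 itself fixes.

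The 14 months is an expectation. Slower accrual would leave some enrolment to influence, though most participants would still be randomized (step 4).

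Finally, one might conclude that the efficacy boundary and its 5% allowance should go. That does not follow. The look leaves the final test near 0.049, so it costs little. Removing the allowance would cut the sample to about 124 per arm (103 × 1.2), or 248, in a trial that expects up to 15% withdrawal, all counted as non-response.

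**Conclusion.** The point holds as a mismatch between timing and purpose. On planned accrual, the only scheduled between-arm review falls 0.8 to 1.0 month after the last randomization, with about 27 of 260 participants (11%) still in the treatment window. It cannot reduce the number randomized and can spare very few people randomized instillations. Its ethical purpose is therefore largely but not wholly defeated.

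This rests on roughly uniform accrual at the stated pace. A slow start makes it worse; clearly front-loaded accrual, or an accrual period longer than about 15.6 months, eases it. The fifteen-month figure is not an error, and the 0.0031 boundary is correct. What needs changing is the date of the between-arm safety comparison, which has no need to wait for week 34.

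**What to change.** In Section 13.5.1:

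- Add a closed between-arm review by the External Advisory Committee of toxicity, adverse events and withdrawals when early cohorts complete the treatment phase, for example the first 65 and first 130 participants at week 10 (about months 5.8 and 9.3). Specify no efficacy test at these reviews, so that no alpha is spent. The cohort sizes are a suggestion; the principle is that the review should come while enrolment is open.
- Keep the week-34 efficacy look at 0.0031 and the sample of 260.
- State that, on planned accrual, the week-34 look can affect only ongoing follow-up, the last instillations and open-label Phase 2, not enrolment.

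The cost is a change of wording and one or two extra closed reports. No extra participants are needed, and the final test is unchanged.

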### 13.5.2 Final Analysis

Details of the final analysis of the data will be provided in the Data Analysis and Monitoring Plan (DAMP).

## 13.6 Statistical Computing

The appropriate ASCII and SAS data files will be extracted from the Oracle database for use in statistical analysis. Primary analyses, including graphical methods, will be implemented using various commercially available statistical packages including SAS (54-61) and S-plus (62). The Proc-StatXact for SAS Users software (48) will be used to compute the exact tests of discrete measures between groups. All software is currently available through the networked computing environment within the DCC.

## ICCTG Protocol #2 – Visit Schedule (Weeks) Phase I – Randomized, Double-Blind Study

## **APPENDIX B**

		ening sits	Treatment Phase 6 Treatments in 10 Weeks				Post-Treatment Follow-up Phase 24 Weeks (6 Months)								
			RX	RX	RX	RX	RX	RX	Phone Visit	Phone	Clinic	Phone	Clinic	Phone	Clinic
Event	B1 -4	B2 -1	1	2	3	4	5 *	6 *	(optional)	Visit	Visit 18	Visit 22	Visit 26	Visit 30	Visit 34
Week	-4	-1	1*	*	*	*	*	*	10, 11, or 12	14					
Visit Number	1	2	3	4	5	6	7	8	9	10	11	12	13	14	15
Consent Form	Χ														
Clinic Visit	Χ	Χ	Χ	Χ	Χ	Χ	Χ	Χ			Χ		X		Χ
Treatment Follow-Up Phone Call									~	~		~		*	
Day 1 Follow-up (PHNTP)			2	A		A									
Day 2 Follow-up (PHNTP)			*	A		A									
Patient Contact Information (PTCONT)	Χ														
Medical History (MED)	Χ														
Voiding Diary (VOID)		$X^3$									$X^3$		$X_3$		$X^3$
Demographics (DEMO)	Χ														
Eligibility Confirmation (ELIG)	Χ	Χ													
Randomization (RAND)		Х													
Patient's Daily Medication Diary (PTDIARY)	X 3	X 	X 	X 	$X_3$	X 	$X_3$	X 			X³				X 3
Medication Diary Record (CMED)		Х	Х	Х	Х	Х	Х	Х			Х				Х
Instillation/Dosing Information (DOSE)			Х	Х	Х	Х	Х	Х							
Adverse Event/Serious Adverse Event (AE)			Х	Х	Х	Х	Х	Х	Х	Х	Х	Х	Х	Х	Х
Contraceptive Use (DOSE and STVISIT)			Х	Х	Х	Х	Х	Х	Х	Х	Х	Х	Х	Х	Х
Unmasking Record (UNMASK) 															-
Treatment Stop Point I (TSTOPI) 								Χ							·
Study Stop Point I (SSTOPI) 															X
Patient Transfer (TRANS) 															
Study Close-out (STCL) 															X
Patient Close-out (PTCL) 															Х
SYMPTOM QUESTIONNAIRES:															
Baseline Symptoms (BSYM1&2)	Х	Х													
Follow-up Symptoms (FUSYM)								Χ			Х		Χ		Х
IC Symptom & Problem Index (SYMPROB)		Х						Х			Х		Х		Х
Health Status Questionnaire (SF36)		Х		1				Χ			Х		Χ		Х
MOS Sexual Functioning Scale (MOS)		Χ						Χ			Х		Х		X

\* The six treatments are to be given within a ten-week period. The first instillation must occur as soon as possible after randomization, but no later than two weeks after randomization. No instillations will be given after Week 10. No more than three weeks and no less than six days may elapse between instillations. 2=At baseline and PRN. 3=Diaries to be handed out at B1 are collected at B2. Diaries collected at subsequent clinic visits will be given to the patient at the previous clinic visit. 4=When indicated. 5=Urine biomarker samples will be collected during catheterization on treatment visits 1 and 4 just before treatment. Voided samples will be collected 6 hours after the fourth treatment and at the 6-month post-treatment visit.

Page 1 of 4 05/28/02

ICCTG Protocol #2 – Visit Schedule (Weeks) Phase I – Randomized, Double-Blind Study

## **APPENDIX B**

	Scree Vis	_		Treatment Phase 6 Treatments in 10 Weeks					Post-Treatment Follow-up Phase 24 Weeks (6 Months)						
Event	B1	B2	RX 1	RX 2	RX 3	RX 4	RX 5	RX 6	Phone Visit (optional)	Phone Visit	Clinic Visit	Phone Visit	Clinic Visit	Phone Visit	Clinic Visit
Week	-4	-1	1*	*	*	*	*	*	10, 11, or 12	14	18	22	26	30	34
Visit Number	1	2	3	4	5	6	7	8	9	10	11	12	13	14	15
U. of Wis. Symptom Survey (UNIVWIS)		Х						Х			X		X		Х
LABS & PROCEDURES															
Urine Screening: Culture  (URINE)	Χ														Χ
Urine Screening: UA (DOSE/URINE)	Χ		Χ	Χ	Χ	Χ	Χ	Χ							Χ
Physical Exam (EXAM)		Χ													X
Serum ß-HCG Pregnancy Test  (LAB)	Χ														Χ
Pelvic/DRE (EXAM)		Χ													
Blood: CBC (LAB) 	Χ														Χ
Urine Sample Tracking (for Banking/Biomarkers) Urine Tracking (UTRAC)  Participant Urine Tracking (PUTRAC) 			Х			X X									Х
Temperature (PHNTP)			Χ	Х	Х	Х	Х	Χ							

Page 1 of 4 05/28/02

\* The six treatments are to be given within a ten-week period. The first instillation must occur as soon as possible after randomization, but no later than two weeks after randomization. No instillations will be given after Week 10. No more than three weeks and no less than six days may elapse between instillations. 2=At baseline and PRN. 3=Diaries to be handed out at B1 are collected at B2. Diaries collected at subsequent clinic visits will be given to the patient at the previous clinic visit. 4=When indicated. 5=Urine biomarker samples will be collected during catheterization on treatment visits 1 and 4 just before treatment. Voided samples will be collected 6 hours after the fourth treatment and at the 6-month post-treatment visit.

## ICCTG Protocol #2 – Visit Schedule (Weeks) Phase II – Open-Label Study

## **APPENDIX B**

	Treatment Phase 6 Treatments in 10 Weeks				Post-Treatment Follow-up Phase 24 Weeks (6 Months)								
Event	RX 1	RX 2	RX 3	RX 4	RX 5	RX 6	Phone Visit (optional)	Phone Visit	Phone Visit	Phone Visit	Phone Visit	Phone Visit	Clinic Visit
Week	35*	*	*	*	*	*	44, 45 or 46	48	52	56	60	64	68
Visit Number	16	17	18	19	20	21	22	23	24	25	26	27	28
Clinic Visit	Χ	Х	Х	X	Х	X							Х
Treatment Follow-Up Phone Call							~	~	~	~	~	~	
Day 1 Follow-up (PHNTP)		~	A		A	A							
Day 2 Follow-up (PHNTP)		~	A		A	A							
Voiding Diary (VOID)													$X^3$
Patient's Daily Medication Diary (PTDIARY)	$X^3$	$X_3$	$X_3$	$X^3$	$X_3$	$X^3$			$X^3$				
Concomitant Medication (CMED)	Χ	Х	Х	Х	Х	Х			X				X
Instillation Dosing Information (DOSE)	Χ	Х	Х	Х	Х	Х							
Adverse Event/Serious Adverse Event (AE)	Χ	Х	Х	Х	Х	Х	X	X	X	Х	Х	X	X
Contraceptive Use (DOSE/STVISIT)	Χ	Χ	Χ	Χ	Χ	Χ	X	X	X	X	X	X	X
Unmasking Record (UNMASK) 													
Treatment Stop Point II (TSTOPII)4						Χ							
Study Stop Point II (SSTOPII) 													X
Patient Transfer (TRANS) 													
Study Close-out (STCL) 													Χ
SYMPTOM QUESTIONNAIRES:													
Follow-up Symptoms (FUSYM)													Х
IC Symptom & Problem Index (SYMPROB)													Х
Health Status Questionnaire (SF36)													Х
MOS Sexual Functioning Scale (MOS)													Х
U. of Wis. Symptom Survey (UNIVWIS)													Х
LABS & PROCEDURES													
Urine Screening: Culture (URINE) 4													Χ
Urine Screening: UA (DOSE/URINE)	Х	Х	Х	Х	Х	Х							Х
Physical Exam (EXAM)													Х
Serum ß-HCG Pregnancy Test  (LAB)													Х
Blood: CBC (LAB) 													Х
Temperature (PHNTP)	X	Х	Х	Х	Х	Х	_						

\* The six treatments are to be given within a ten-week period. The first instillation must occur as soon as possible after randomization, but no later than two weeks after randomization. No instillations will be given after Week 10. No more than three weeks and no less than six days may elapse between instillations. 2=At baseline and PRN. 3=Diaries to be handed out at B1 are collected at B2. Diaries collected at subsequent clinic visits will be given to the patient at the previous clinic visit. 4=When indicated. 5=Urine biomarker samples will be collected during catheterization on treatment visits 1 and 4 just before treatment. Voided samples will be collected 6 hours after the fourth treatment and at the 6-month post-treatment visit. Page 3 of 4

ICCTG Protocol #2 – Visit Schedule (Weeks)

